391 control clusters of 10-40%, a range of 350-1000 persons in each cluster for HIV-negative
392 outcomes, an RDS design effect of 2, a two-sided α of 0.05, power=0.80 and a within-stratum
393 coefficient of variation ranging from 0.10 to 0.40. We incorporated the RDS design effect
394 (relative to simple random sampling) by doubling the sample size required per cluster after
395 calculating power. For the primary outcome, with 11 intervention and 11 control clusters, we
396 will have 80% power to detect an absolute difference of 12% in the prevalence of the primary
397 outcome in intervention and control clusters (e.g., 42% and 30%, respectively) with a within-
398 stratum coefficient of variation of 0.25 and 1000 participants in each cluster.

399 Our trial was powered to be able to detect differences in the primary outcome, but we
400 also calculated power for secondary outcomes. Power for secondary outcomes that include the
401 full sample (e.g., proportion of PWID reporting sharing injection equipment in the prior 6
402 months) was similar to that for primary outcomes as the methods and the range of outcome
403 prevalence in control clusters was within the range of what was considered for the primary
404 outcome. Power was relatively insensitive to the within-cluster sample size so our ability to
405 detect outcome differences for outcomes where only HIV positive subjects are considered is
406 similar to outcomes where the full RDS sample is used. For outcomes restricted to HIV-positive

407 subjects, we assumed a sample size of 100-300 persons per cluster. Power remained insensitive
408 to the cluster sample size down to a sample size of 100 per cluster. For example, with all other
409 assumptions held constant and an RDS sample size of 150, if the baseline prevalence of the
410 outcome is 30%, we will be able to detect a difference of 14 percentage points (e.g., 30% vs.
411 44%). For outcomes with lower baseline prevalence, we would be able to detect a smaller
412 difference (e.g., if 20% of HIV infected patients are engaged in care in the control sites, we
413 would have adequate power to detect a difference of 9 percentage points [20% vs. 29%]).

414

415 **Analysis plan**

416 *Community level.*

417 The primary analysis will be to compare the prevalence of community-level outcomes
418 across intervention and control clusters, adjusting for pre-intervention prevalence levels. For a

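### The 20% vs 29% example for HIV-positive outcomes has about 72% power at 150 per cluster, not the 80% target, and power does depend on cluster size down to 100

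*Combined protocol and SAP*

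**What the plan says.** The Statistical power section sets the general assumptions: "outcomes, an RDS design effect of 2, a two-sided α of 0.05, power=0.80 and a within-stratum" coefficient of variation between 0.10 and 0.40. The design effect is applied by doubling the sample size needed per cluster. The primary example is 30% vs 42% with 11 clusters per arm, a "stratum coefficient of variation of 0.25 and 1000 participants in each cluster".

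For the HIV-positive outcomes the section makes four statements:

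- The ability to "detect outcome differences for outcomes where only HIV positive subjects are considered is" described as similar to that for the full sample.
- On size: "subjects, we assumed a sample size of 100-300 persons per cluster. Power remained insensitive" "to the cluster sample size down to a sample size of 100 per cluster".
- First example: with other "assumptions held constant and an RDS sample size of 150, if the baseline prevalence of the" outcome is 30%, a 14-point difference (30% vs 44%) is detectable.
- Second example, in the next sentence and with engagement in care as the illustration: the trial "would have adequate power to detect a difference of 9 percentage points [20% vs. 29"%].

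The second example restates neither a cluster size nor a coefficient of variation.

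**The concern.** The two HIV-positive examples appear to share the same inputs, so one formula should give both. It does not.

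A claim of insensitivity to cluster size is reasonable when between-cluster variation dominates, as it does with 1000 per cluster. It is less plausible with 100 to 300 per cluster, halved by the design effect, and at a low prevalence, where binomial error is large relative to the between-cluster term.

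Hypothesis 2 (access to care, ART use, community viral load) rests on HIV-positive denominators. Some Table 1 outcomes use narrower ones still, such as ART-eligible participants or those with CD4 below 200. The failing example is the plan's own care-engagement case. A reader who takes a 9-point effect as covered could over-interpret a null result on these outcomes.

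**Working it through.** **Inputs (Statistical power section).** c = 11 clusters per arm; two-sided alpha 0.05 (z = 1.960); target power 0.80 (z = 0.8416); coefficient of variation k = 0.25; design effect 2, so N sampled counts as m = N/2. The values N = 150 and k = 0.25 for the 20% vs 29% example are carried over from the sentences before it.

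**Formula.** The plan cites a textbook but prints no formula. I assume the standard unmatched form for two proportions:

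c = 1 + (1.960 + 0.8416)² × [p0(1−p0)/m + p1(1−p1)/m + k²(p0² + p1²)] / (p1−p0)²

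Power at c = 11 is Φ( |p1−p0| × √(10/V) − 1.960 ), where V is the bracketed term.

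**Plan's figures that reproduce.**

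- 30% vs 42%, N = 1000 (m = 500): V = 0.000907 (within) + 0.016650 (between) = 0.017557. Clusters needed 10.57; power 81.7%.
- 30% vs 44%, N = 150 (m = 75): V = 0.006085 + 0.017725 = 0.023810. Clusters needed 10.53; power 81.8%. The difference detectable with 80% power is 13.6 points, against 14 stated.

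**The figure that does not.**

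- 20% vs 29%, N = 150 (m = 75): V = 0.16/75 + 0.2059/75 + 0.0625 × (0.04 + 0.0841) = 0.004879 + 0.007756 = 0.012635.
- Clusters needed = 1 + 7.849 × 0.012635/0.0081 = 13.24, against 11 available.
- Power = Φ(0.09 × √(10/0.012635) − 1.960) = Φ(2.532 − 1.960) = Φ(0.572) = 71.6%.
- The difference detectable with 80% power from 20% is 10.15 points. A flat 20% vs 30% has 79.0%.

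**Variants for 20% vs 29% at N = 150.** No added cluster, 75.7%; t-based with 20 df, 71.4%; log scale, normal, 76.5%; log scale, t, 72.3%; t-based with the added cluster, 67.3% (66.8% on 18 df). All are below 80%.

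**What would rescue it, and the effect on the other examples.**

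- Design effect omitted (m = 150): 80.5%. The detectable difference at 30% would then be 12.5 points, not 14.
- k of about 0.209 at N = 150: 80%. The detectable differences at 30% would then be 11.8 points at N = 150, not 14, and 9.6 points at N = 1000, not 12.
- N of about 285 at k = 0.25: 80%. That is near the top of the assumed 100–300 and is not the 150 just stated.
- Between-cluster SD held at the control-arm value: 81.7%. That version gives 93.1% for the primary example and 92.0% for 30% vs 44%, so it fits neither.

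**Sensitivity to cluster size (k = 0.25, design effect 2).**

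| HIV-positive per cluster | Power, 20% vs 29% | Power, 30% vs 44% | Detectable difference from 20% | Detectable difference from 30% |
|---|---|---|---|---|
| 300 | 80.5% | 86.7% | 8.9 points | 12.5 points |
| 150 | 71.6% | 81.8% | 10.1 points | 13.6 points |
| 100 | 64.0% | 77.1% | 11.2 points | 14.6 points |

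The within-cluster share of V explains the pattern. It is 5.2% in the primary example (0.000907/0.017557), 38.6% for 20% vs 29% at N = 150 (0.004879/0.012635), and 48.5% at N = 100 (0.007318/0.015074). Even with the design effect left out, power for 20% vs 29% falls from 85.2% at 300 to 75.9% at 100.

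**The case against.** Five points can be made for the plan.

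1. **Inputs.** The 20% vs 29% sentence gives no cluster size, no coefficient of variation and no 80%; it claims only adequate power. Within the section's stated ranges it can hold, for instance at 300 per cluster or at k = 0.20 (81.8% at 150). This stands as a caveat. However, the sentence continues the 150-per-cluster example, 0.80 is the only power target given, and none of the alternatives I tried fits all three printed examples.

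2. **Formula.** It is inferred, so 72% is not exact. This also stands: the shortfall could be 3 to 13 points. Its direction does not change.

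3. **Insensitivity is a matter of degree.** For 30% vs 44% the fall from 300 to 100 per cluster is 9.6 points, and without the added cluster power at 100 is still 80.9%. The plan also shows some cost itself, moving from 12 points at 1000 to 14 at 150. That softens the criticism for the 30% case. It does not cover 20% vs 29%, where the fall is 16.5 points.

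4. **Baseline adjustment.** The planned analysis adjusts for pre-intervention prevalence, which may lower the effective k. Reaching 0.209 from 0.25 needs about a 30% cut in between-cluster variance (1 − 0.209²/0.25² = 0.30). The power section claims no such gain, but the unadjusted miss rate should not be presented as that of the final analysis.

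5. **Consequence.** The trial was powered on its primary outcome, and clusters and survey size are fixed. True; this limits the matter to how the secondary results are read.

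**Conclusion.** The concern holds. On the natural reading (150 per cluster, k = 0.25, design effect 2), 20% vs 29% has about 72% power, with a range of 67% to 77% over formula variants, against a target of 80%. The chance of missing a true 9-point effect in an unadjusted comparison is about 28% at 150 per cluster and 36% at 100. The detectable difference is about 10 points rather than 9.

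The insensitivity statement is not supported over the assumed range of 100 to 300, most clearly at 20% prevalence. These results rest on the inferred formula, which two of the plan's three examples confirm, and on the carried-over cluster size and coefficient of variation. The primary-outcome power statement reproduces and is not in question.

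**What to change.** Restate the examples along these lines: with 150 HIV-positive participants per cluster, design effect 2 and coefficient of variation 0.25, there is 80% power for 30% vs 44% and for 20% vs about 30%; detecting 20% vs 29% needs about 285 per cluster. If the 20% vs 29% figure came from other inputs, state them instead and bring the 30% example into line.

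Replace the insensitivity sentence, and the statement that power is similar to the full sample, with the detectable differences at 300, 150 and 100 per cluster: 8.9, 10.1 and 11.2 points from 20%, and 12.5, 13.6 and 14.6 points from 30%. Put the cluster size and coefficient of variation beside every example. Say that any gain from baseline adjustment is not counted.

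The cost is wording and recomputed figures only. Clusters, sample size and analysis do not change. The stated power for HIV-positive outcomes becomes slightly less favourable.

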253 population in question, and had no stake in the outcome of the ICC evaluation. Interviewers
254 recorded answers to a web-based, secure database via laptops and a local area network. RDS
255 interviewers and support staff were trained extensively on visit flow, documentation,
256 questionnaires, and laboratory procedures using a single training protocol across sites. Quality
257 control for the survey was maintained by programmed logic checks and real-time data
258 monitoring algorithms and by site supervisors who monitored 5% of randomly selected
259 interviews for proper interviewing technique. Constraints placed on the database required
260 interviewers to answer every question on the survey and ensured that missing data was minimal.

261 Participants were also asked to recruit up to two members of their sexual (MSM) or drug-
262 using networks (PWID) who satisfied the study eligibility criteria using bar-coded coupons that
263 had a holographic image to hinder replication attempts. If participants successfully referred
264 eligible participants, they received an additional incentive of INR 50 (USD 0.8) per eligible
265 person recruited in addition to compensation of INR 250 (USD 4.1) for completing the pre-
266 intervention assessment. Participants were recruited in successive RDS waves at each site until
267 the desired sample size was accrued.

268

269 *Randomization.*

270 Randomization took place after the pre-intervention assessment was completed. First, we
271 selected 12 PWID sites (from 15) and 10 MSM sites (from 12) for randomization. In the PWID
272 stratum, two sites were removed because of logistical challenges that deemed them unsuitable for
273 randomization (Moreh, Gangtok). Three additional sites were dropped based on very low HIV
274 prevalence (Bhubaneswar [PWID-stratum], Lucknow and Mangalore [MSM-stratum]).

275 We used a restricted stratified randomization approach to randomly distribute the 22 sites
276 to either the intervention or control condition [53]. In CRTs, the number of randomized units is
277 relatively small and large imbalances between study arms may occur if randomization is
278 unrestricted; hence, restricted randomization is often used to ensure reasonable balance between
279 study arms in important factors. However, the desire for balance between arms must be balanced
280 against leaving a sufficient number of randomization options (e.g., at least 100).

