419 given outcome, we will first log-transform the 22 cluster-level proportions obtained from the
420 post-intervention RDS. Then, via weighted least squares linear regression, these will be
421 regressed on a dummy term for the control arm (vs. intervention), another for the MSM stratum
422 (vs. PWID), and a term for the log-transformed cluster-level pre-intervention proportions. The
423 exponentiated coefficient for the control arm term is thus the prevalence risk ratio (PRR), and $(1-$
424 $PRR) \times 100\%$ is the percentage increase in service utilization associated with the intervention.
425 The primary analyses will be conducted using the RDS-II weighted cluster-level proportions
426 from both pre- and post-intervention RDS samples. These RDS-II weights, which account for
427 personal network size (number of PWID or MSM seen in the past 30 days) will be calculated
428 using the RDS Analyst Software Version 0.5 (<http://hpmrg.org>). For secondary outcomes that are
429 continuous (e.g., community viral load) we will use a similar regression approach.

430 We will conduct several sensitivity analyses for the primary and all secondary outcomes
431 First, we will repeat analyses using unweighted cluster-level proportions from both the pre-and
432 post intervention RDS surveys. Second, we will consider adjustment for demographic covariates
433 (age, sex, marital status and educational attainment) measured at the post-intervention RDS that
434 are associated with the outcome and are differentially distributed across intervention and control
435 clusters. We will consider adjustment for these factors if the p values for associations with the
436 outcome and the intervention vs. control clusters are <0.05 and the OR is >2 or <0.5 . A two-
437 stage approach will be used when adjusting for individual-level covariates: at the first stage, for a
438 prevalence outcome, individual responses are modeled with a logistic regression model adjusting
439 for all relevant covariates except the dummy term for control vs. intervention. In the second
440 stage, observed and expected prevalence counts for each cluster are calculated, followed by t-
441 test-like analyses of log-transformed ratios of observed to expected [53]. We will also consider
442 an approach that models the difference in outcome prevalence between the pre- and post-
443 intervention surveys using the same cluster-level comparison approach. We will also consider

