Awareness of HIV status, access to care, and HIV treatment				
2	Awareness of HIV status among HIV-seropositive persons	1. Survey 2. Serologic HIV test	HIV seropositive participants	Reports having a positive HIV test OR being told by a doctor that he/she had HIV.
3	Accessing HIV medical care in prior 6 months	1. Survey 2. Serologic HIV test	HIV seropositive participants	Reports seeing a doctor about HIV AND reports visit with the indicated doctor in the prior 6 months.
4	Use of ART among ART-eligible	1. Survey 2. Serologic HIV test	HIV seropositive participants who meet either criteria 1 or 2 1. Reports taking ART at any time in the past OR 2. CD4 <350 cells/ μ L	Reports ART use in prior 30 days.
5	Use of trimethoprim-sulfamethoxazole (TMP-SMX) when indicated	1. Survey 2. Serologic HIV test 3. CD4	HIV seropositive AND CD4 count < 200 cells/ μ L	Reports taking TMP-SMX in past 30 days
6	Viral suppression among ART-eligible	1. Survey 2. Serologic HIV test 3. CD4 4. HIV RNA	HIV seropositive participants who meet either criteria 1 or 2 1. Reports taking ART at any time in the past OR 2. CD4 <350 cells/ μ L	HIV RNA <150c/mL
7	Viral suppression among HIV-positive	1. Serologic HIV test 2. HIV RNA	HIV seropositive participants	HIV RNA <150c/mL
8	Average CD4 cell count among HIV-positive	1. Serologic HIV test 2. CD4 cell count	HIV seropositive participants	CD4 cell count

Table 1. Outcome definitions for the Indian National Collaboration on AIDS (NCA) study

	Outcome	Data inputs	Population (denominator)	Definition
Risk behaviors, substance use, and depression				
9	Unprotected anal intercourse with non-main male partner in prior 6 months [MSM]	Survey	Participants at MSM sites	Does not report “always” using a condom during insertive or receptive anal sex with non-main (e.g., casual, one-time partner, sex worker) male partners in the prior 6 months
10	Number of non-main male sexual partners in prior 6 months [MSM]	Survey	Participants at MSM sites	Number of non-main male (e.g., casual, one-time partner, sex worker) male partners with whom the participant reports having insertive or receptive anal sex in the prior 6 months
11	Symptoms of sexually transmitted infection [MSM]	Survey	Participants at MSM sites	Reports genital/anal discharge, pain, or ulcer in prior 6 months
12	Syphilis infection	1. RPR test 2. TPHA test	Participants at MSM sites	Positive for syphilis infection by both RPR and TPHA tests

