26	HIV incidence	1. Serologic HIV test 2. HIV RNA 3. CD4 cell count 4. BED assay 5. Avidity index	Participants who meet criteria 1 or 2 1) HIV-seronegative OR 2) HIV-seropositive participants who meet criteria for recent infection by HIV RNA, CD4, BED assay, and avidity assay	Cross-sectional HIV incidence estimated as described previously[64, 7, 6]

Table 2. Data Collection

	MSM	PWID
Survey modules		
Demographics	X	X
Peer network size	X	X
HIV testing, care and medications (HIV care continuum)	X	X
HIV treatment knowledge (including questions on other local HIV testing and treatment efforts)	X	X
Substance use (drugs, alcohol), injection-related risk behavior, sexual risk behavior	X	X
Service utilization (NSEP, OST, condom provision)	X	X
Tuberculosis history	X	X
Depressive symptoms (Patient Health Questionnaire-9 [65, 62])	X	X
Social support	X	X
Stigma (Enacted, vicarious, felt normative, internalized MSM stigma)	X	
Stigma (Enacted, vicarious, felt normative, internalized PWID stigma)		X
Quality of life (adapted version of EuroQOL [66])	X	X
Acceptability of novel prevention interventions (early ART, circumcision, PrEP)	X	X
Sexual health (including STI history)	X	
Hepatitis C virus and Hepatitis B virus testing, care and treatment		X
Laboratory testing		
HIV ⁸		
Determine HIV 1/2, Alere Medical Co., Ltd., Chiba, Japan	X	X
First Response HIV Card Test 1-2.0, PMC Medical India Pvt, Ltd, Daman, India		
Signal Flow Through HIV 1+2 Spot/Immunodot Test kit, Span Diagnostics Ltd, Surat, India		
CD4 count*	X	X
Flow cytometry, Epics XL – MCL, Beckman Coulter Inc., USA		
HIV RNA*	X	X
RealTime HIV-1 Assay, Abbott Laboratories, Abbott Park, Illinois, USA		
BED assay*	X	X
Aware TM BED TM EIA HIV-1 Incidence Test (IgG Capture HIV-EIA), Calypte Biomedical Corporation, Portland, OR, USA		
Avidity[67]*	X	X
GS HIV-1/HIV-2 PLUS O EIA, Biorad Laboratories, Redmond, USA using diethyl amine as the chaotropic agent		
HSV-2	X	
Anti-HSV-2 (gG2) ELISA (IgG), Euroimmun Medizinische Labordiagnostika AG, Lubeck, Germany		
Syphilis	X	
RPR Test Kit, Span Diagnostics Ltd. Surat, India		
Immunotrep TPHA, Omega Diagnostics Limited, Scotland, UK		

Abbreviations: NSEP, Needle and syringe exchange programs ; OST, Opioid substitution therapy ;MSM, Men who have sex with men; PWID, People who inject drugs; ART, Antiretroviral therapy; PrEP, Pre-exposure prophylaxis; STI, Sexually transmitted infections

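### The community-level model takes logs of city proportions and has no rule for a city with zero events; HIV incidence, TMP-SMX use and small subgroups are exposed

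*Combined protocol and SAP*

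**What the plan says.** The Analysis plan (Community level) describes one main model. For a "given outcome, we will first log-transform the 22 cluster-level proportions obtained from the" post-intervention survey. These values are regressed by weighted least squares on arm, stratum and the baseline value, which is also logged: "vs. PWID), and a term for the log-transformed cluster-level pre-intervention proportions. The". The weights of the least-squares fit are not defined. For outcomes that are "continuous (e.g., community viral load) we will use a similar regression approach", no log is explicitly required.

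Two secondary outcomes in Table 1 have small numerators or denominators:
- **Outcome 5.** The denominator is "HIV seropositive AND CD4 count < 200" cells/µL, and the event is "Reports taking TMP-SMX in past 30 days".
- **Outcome 26.** The definition is "Cross-sectional HIV incidence estimated as described previously". Its events are the few seropositive persons whom a multi-assay algorithm classes as recently infected.

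For outcomes in HIV-positive persons, the Statistical power section says: "subjects, we assumed a sample size of 100-300 persons per cluster. Power remained insensitive". The plan also calls for analyses of all outcomes within strata and within subgroups, which makes denominators smaller.

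The document gives no continuity correction, exclusion rule or alternative model for a zero.

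**The concern.** The log of zero is undefined. One zero at either survey leaves that city without a usable record, so the stated model cannot be fitted to all 22 cities.

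The planned sensitivity analyses do not close the gap. The unweighted repeat meets the same zeros, because a city with no events is zero with or without RDS weights. The two-stage observed-to-expected analysis also takes logs. The pre-post difference analysis and the multilevel models can accept zeros, but the plan only undertakes to consider them and sets no trigger.

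So the rule would be chosen after someone has seen which cities are zero and in which arm. HIV incidence is part of hypothesis 3. If zero cities were simply left out, those with the best incidence result would be the ones lost, and more of them would come from the arm with the lower rate.

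**Working it through.** **Nearest planning figure.** The documents give no figure on zero-event cities. The closest is 80% power for the primary outcome: 30% vs 42%, 11 cities per arm, coefficient of variation k = 0.25, 1000 persons per city and design effect 2, so 500 effective persons.

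c = 1 + (1.96 + 0.84)² × [p0(1−p0)/n + p1(1−p1)/n + k²(p0² + p1²)] / (p1−p0)²
= 1 + 7.85 × [0.00042 + 0.00049 + 0.01665] / 0.0144 = 10.57, rounded up to 11.

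Power with 11 per arm is 81.7%, so the figure reproduces.

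**Primary outcome.** At the lowest planned prevalence, 10%, P(zero in a city) = 0.9^500, about 1e-23. There is no practical risk.

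**HIV incidence.** Assumptions, not in the documents: 700-900 HIV-negative persons per city, 0.5-1 per 100 person-years, window 0.3-0.5 years.
- Expected recent infections per city: from 700 × 0.005 × 0.3 = 1.05 to 900 × 0.01 × 0.5 = 4.5.
- Expected zeros among 44 city-surveys, 44 × exp(−μ): 44 × exp(−1.05) = 15.4, and 44 × exp(−4.5) = 0.5.
- At 2 per 100 person-years, μ is at least 700 × 0.02 × 0.3 = 4.2, and 44 × exp(−4.2) = 0.66, so under one zero is expected.

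**TMP-SMX.** The plan assumes 100-300 HIV-positive persons per city. The share with CD4 below 200 and the level of use are assumptions. P(zero) = (1−u)^m for m eligible persons and use u; the chance of at least one zero in 44 is 1 − (1 − P)^44.

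| Eligible per city | Use | P(zero) per city | At least one zero in 44 |
|---|---|---|---|
| 30 | 10% | 0.042 | 85% |
| 30 | 20% | 0.001 | 5% |
| 15 | 20% | 0.035 | 79% |
| 15 | 40% | 0.0005 | 2% |

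**Bias if zero cities are dropped.** For Poisson counts X, the ratio recovered is exp(E[log X | X>0, intervention] − E[log X | X>0, control]). With a true ratio of 0.50:

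| Expected events per control city | Ratio recovered |
|---|---|
| 1.5 | 0.77 |
| 2.7 | 0.64 |
| 4 | 0.56 |
| 5 | 0.52 |
| 6 | 0.50 |
| 8 | 0.48 |

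At 2.7, the expected number of cities lost is 11 × exp(−1.35) = 2.9 in the intervention arm and 11 × exp(−2.7) = 0.7 in the control arm.

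**Simulation of the regression** (22 cities; arm, stratum and baseline terms; k = 0.25; true ratio 0.50; unweighted log models):

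| Expected events per control city | Zero cities dropped | 0.5 added to every count | Quasi-Poisson, all 22 cities |
|---|---|---|---|
| 1.5 | 0.77 | 0.63 | 0.49-0.50 |
| 2.7 | 0.65 | 0.55 | 0.49-0.50 |
| 4 | 0.57 | 0.52 | 0.49-0.50 |

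A repeat of 1,500 runs, averaged on the log scale, gave 0.47, 0.48 and 0.49 for quasi-Poisson. Its type I error was near 4%.

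At 2 events per control city, dropping leaves 13.8 cities on average and 18% power; adding 0.5 gives 35%. With no true effect, dropping gives a ratio near 1.00 and rejection of 4.5-6.9%. If the least-squares weights are the event counts, the dropped-city estimate runs from 0.79 at a control mean of 1 to 0.53 at 10, so the undefined weights also affect the size of the bias.

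**The case against.** The strongest reply is that this is a missing edge-case rule for a few secondary outcomes in a trial powered for another endpoint. Several points support that view.

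- **Scope.** A reader might infer that every outcome is at risk. The log rule is stated for proportions. CD4 count, mean log10 RNA, number of partners and stigma scores are not proportions, and the primary outcome is safe.
- **Dropping cities.** A reader might infer that the plan discards zero cities. It does not say so; that is only what software commonly does with a missing log.
- **Direction.** A reader might infer a general bias toward no effect. The bias needs a true effect, post-intervention zeros, dropped cities and low counts. A baseline zero precedes randomization, so losing that city mainly costs power. From about 6 events per city the unweighted estimate is close to the truth, and it then leans slightly the other way.
- **Frequency.** Zeros depend on rates that the documents do not give. Sites were chosen for high HIV prevalence or risk, and some were removed before allocation for the opposite reason: "randomization (Moreh, Gangtok). Three additional sites were dropped based on very low HIV" prevalence.
- **Estimator.** Incidence follows methods in cited sources that cannot be checked here, including how they treat a city with no recent infections.

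All of this narrows the point. It does not supply a rule for zeros, and the analyses that tolerate them remain optional.

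**Conclusion.** The point holds for sparse proportion or rate outcomes: the stated model cannot be computed on all 22 cities when any city has zero events at either survey, and nothing says what happens then. That part rests on the text alone.

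The size is conditional. Under the assumed rates, incidence would have about 0.5 to 15 zeros among 44 values. TMP-SMX could have almost none or several. If zero cities were dropped and the true ratio were 0.50, the estimate would be pulled to about 0.77 to 0.57 at 1.5 to 4 expected events per control city, with a clear loss of power. There is no bias under no effect, and little from about 6 events per city unless count weights are used, when some attenuation remains (about 0.55 at 6).

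The documents do not support a claim that the trial's main result is threatened. The change is worth making because HIV incidence is a named hypothesis and a model that accepts zeros performs better than either dropping cities or adding a constant.

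**What to change.** Before the post-intervention data are analysed, add a short paragraph to the Analysis plan that does the following:

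1. Names the sparse outcomes in advance: at least 5 and 26, plus any outcome (or planned subgroup of one) with a zero or very low city count at the baseline survey, which has already been observed.
2. Analyses these with all 22 cities by a cluster-level log-link quasi-Poisson regression, so that the effect remains a ratio. The response is the RDS-II weighted city proportion or rate, or weighted counts with a log denominator offset. The terms are arm, stratum and the untransformed baseline value. Inference uses t with 22 − 4 = 18 degrees of freedom.
3. States that an observed post-intervention zero does not trigger a change of effect measure.

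The cost is a few sentences and a slightly different model for a few secondary outcomes. The primary outcome analysis does not change. There was still time: the document is dated November 2016, and the post-intervention survey was expected to finish by April 2017.
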